5.1.3. Visit 3: Day 8 ± 1 day – Diary Collection

This visit will occur on Day 8 ± 1 day as calculated from Visit 2: Day 1, and the following evaluations will be performed:

- Use of any concomitant medications since the last visit
- Occurrence of any AEs since the last visit
- Subject-rated assessment of ocular discomfort
- [REDACTED]
- Used and unused double-masked investigational product counted and compliance assessed [REDACTED]
- [REDACTED]

Instructions to subject:

- Dose investigational product as instructed.
- [REDACTED]
- [REDACTED]
- Return for Visit 4 on Day 15 ± 1 day.

5.1.4. Visit 4: Day 15 ± 1 day – Study Visit

This visit will occur on Day 15 ± 1 day as calculated from Visit 2: Day 1, and the following evaluations will be performed/assessed:

- Use of any concomitant medications since the last visit
- Occurrence of any AEs since the last visit
- [REDACTED]
- Used and unused double-masked investigational product collected, counted, and compliance assessed [REDACTED]
- Subject-rated ocular discomfort assessment
- Investigator-rated assessment of signs
- Investigator-rated assessment of bulbar conjunctival hyperemia
- [REDACTED]
- TFBUT
- Corneal fluorescein staining
- BCVA
- Slit-lamp biomicroscopy
- IOP measurement
- Re-supply of double-masked investigational product to last until Visit 6.
- [REDACTED]

Instructions to subject:

- Dose investigational product as instructed.
- [REDACTED]
- [REDACTED]
- Return for Visit 5 on Day 22 ± 1 day.

5.1.5. Visit 5: Day 22 ± 1 day – Diary Collection

This visit will occur on Day 22 ± 1 day as calculated from Visit 2: Day 1, and the following evaluations will be performed:

- Use of any concomitant medications since the last visit
- Occurrence of any AEs since the last visit
- Subject-rated assessment of ocular discomfort
- [REDACTED]

- Used and unused double-masked investigational product counted and compliance assessed ([REDACTED])
- [REDACTED]

Instructions to subject:

- Dose investigational product as instructed.
- [REDACTED]
- [REDACTED]
- Return for Visit 5 on Day 29 ± 1 day.

5.1.6. Visit 6: Day 29 ± 1 day – End of Study Visit

The End of Study visit will occur on Day 29 ± 1 day as calculated from Visit 2: Day 1, and the following will be performed/assessed:

- Use of any concomitant medications since the last visit
- Occurrence of any AEs since the last visit
- UPT for WOCBP
- [REDACTED]
- Used and unused double-masked investigational product collected, counted, and compliance assessed [REDACTED]
- Subject-rated assessment of ocular discomfort
- Investigator-rated assessment of signs
- Investigator-rated assessment of bulbar conjunctival hyperemia
- [REDACTED]
- TFBUT
- Corneal fluorescein staining
- BCVA
- Slit-lamp biomicroscopy
- IOP measurement
- Dilated ophthalmoscopy
- [REDACTED]
- Release of subject from the study

5.1.7. Unscheduled Visit

Any visits or procedures performed beyond those specified within the protocol must be documented in the Unscheduled Visit pages of the eCRF. Unscheduled visits may include but

are not limited to reporting adverse events (AEs), changes in concomitant medications, or ophthalmic assessments as deemed appropriate by an appropriately qualified physician. If the subject is discontinuing study participation at the unscheduled visit, the eCRFs for Visit 6 should be completed rather than the eCRFs for an Unscheduled Visit.

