Following randomization, subjects will return to the clinic for evaluation at Study Visit 3 (Day 8 ± 1 day), Visit 4 (Day 15 ± 1 day), Visit 5 (Day 22 ± 1 day) and Visit 6 (Day 29 ± 1 day). At Visits 3 (Day 8 ± 1 day) and 5 (Day 22 ± 1 day) evaluations will include [REDACTED] and subject-rated assessment of ocular discomfort. A complete study evaluation will be conducted at Study Visits 4 and 6. Subjects will be released from the study at the end of Visit 6 (Day 29 ± 1 day).

Assessments will include

- Investigator-rated assessment of posterior lid margin hyperemia
- [REDACTED]
- Investigator-rated assessment of conjunctival hyperemia
- Investigator-rated assessment of the character of the meibomian glands' contents
- Investigator-rated assessment of the expressibility of the meibomian glands
- Tear film break up time (TFBUT)
- Corneal fluorescein staining

	
• [REDACTED] discomfort assessment• In-clinic subject-rated assessment of ocular discomfort• Best corrected visual acuity (BCVA)• Slit lamp biomicroscopy• Intraocular pressure (IOP) measurement• Dilated ophthalmoscopy
Efficacy Endpoints	
Primary Efficacy Endpoints:
 
Comparison of mean [REDACTED] Severity Assessment Score between the KPI-121 0.25% ophthalmic suspension group and the vehicle group:
 
• Visit 4 (based on the mean score for the 3 days prior to Visit 4) 
Comparison of mean posterior lid margin hyperemia [REDACTED] [REDACTED] at Visit 2 between the KPI-121 0.25% ophthalmic suspension group and the vehicle group:
 
• Visit 4 
Secondary Efficacy Endpoints:
 
Comparison of mean [REDACTED] Severity Assessment Score between the KPI-121 0.25% ophthalmic suspension group and the vehicle group:
 
• Visit 6 (based on the mean score for the 3 days prior to Visit 6) 
Comparison of mean posterior lid margin hyperemia [REDACTED] [REDACTED] at Visit 2 between the KPI-121 0.25% ophthalmic suspension group and the vehicle group:
 
• Visit 6

Exploratory Endpoints:

Comparison of mean investigator-rated assessment of conjunctival hyperemia between the KPI-121 0.25% ophthalmic suspension group and the vehicle group:

- Visit 4
- Visit 6

Comparison of mean investigator-rated character of the meibomian glands' contents between the KPI-121 0.25% ophthalmic suspension group and the vehicle group:

- Visit 4
- Visit 6

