5.1.8. Early Termination Visit

In the event of termination prior to Visit 6, every attempt will be made to ensure that all Visit 6 assessments are performed. If this is not feasible, at least the following should be performed/assessed:

- Use of any concomitant medications since the last visit
- Occurrence of any AEs since the last visit
- Used and unused investigational product collected and compliance assessed [REDACTED]
- Subject-rated assessment of ocular discomfort
- BCVA
- Slit lamp biomicroscopy
- IOP measurement

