9.1.2. Analysis of Efficacy

The primary analysis population will be the Intent-to-Treat (ITT) population, defined as all subjects randomized, for all analyses [REDACTED]

[REDACTED] A subset of efficacy analyses will be examined for the Efficacy Evaluable (EE) population, the definition of which will be outlined in the Statistical Analysis Plan and finalized prior to unmasking of study data pursuant to clinical data review.

The primary analysis of all ophthalmic efficacy measures will be based on the single study eye for each subject.

[REDACTED] Severity
Assessment Score between the KPI-121 0.25% ophthalmic suspension group and the vehicle group at Visit 4 (based on the mean score for the 3 days prior to Visit 2 and Visit 4); and (2) comparison of mean posterior lid margin hyperemia [REDACTED]

[REDACTED] at Visit 2 between the KPI-121 0.25% ophthalmic suspension group and the vehicle group at Visit 4.

Secondary and exploratory efficacy endpoints will be evaluated as elaborated in [Section 3](#).

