9.3. LEVEL OF SIGNIFICANCE

The primary assessment of the dose-response will be evaluated using a 5% level of significance. Since both co-primary endpoints will be required to be significant at the 0.05 level, there is no adjustment needed for multiple comparisons.

All other reported *p*-values will be considered descriptive and hypothesis generating.

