9.4. PROCEDURE FOR ACCOUNTING FOR MISSING, UNUSED, OR SPURIOUS DATA

Any missing, unused, or spurious data will be noted in the final clinical study report. Multiple imputations will be employed to analyze incomplete data sets under the assumption that missing data are, at worst, characterized as missing at random (MAR). The reasons for missing data will be recorded and the impact of these reasons and any treatment group imbalance on the assumption of MAR will be evaluated. Imputation will be carried out only on the co-primary endpoints and time points.

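### Does recording early exits on the Visit 6 eCRF put values from before Day 29 into the Visit 6 results?

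*Combined protocol and SAP*

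**What the plan says.** Section 5.1.7 sends unscheduled procedures to the Unscheduled Visit pages, with one exception, for a subject "discontinuing study participation at the unscheduled visit, the eCRFs for Visit 6 should be completed rather than the eCRFs for an Unscheduled Visit". No study day is attached to the exception. Section 5.1.6 fixes the visit in time: "The End of Study visit will occur on Day 29 ± 1 day as calculated from Visit 2: Day 1".

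Section 5.1.8 treats termination before Visit 6 as a separate Early Termination Visit at which the Visit 6 assessments are attempted. "If this is not feasible, at least the following should be performed/assessed": the short list that follows has no investigator-rated signs, tear film break-up time or corneal staining. Section 5.3 also asks for the Visit 6 assessments when a randomized subject discontinues.

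The endpoints are named by visit. In the Synopsis the secondary symptom score is taken at "Visit 6 (based on the mean score for the 3 days prior to Visit 6". On missing data, Section 9.4 says: "Imputation will be carried out only on the co-primary endpoints and time points". Under Section 9.3, p-values other than those for the co-primary endpoints "will be considered descriptive and hypothesis generating".

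Section 9.1.2 is partly redacted. It refers to a separate SAP for the Efficacy Evaluable population ("the definition of which will be outlined in the Statistical Analysis Plan"), and Section 9.5 refers to a statistical analysis plan as well. No text of a separate SAP is available here.

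**The concern.** The label and the timing can disagree. A subject who leaves at an unscheduled visit on Day 5 has data on the form for Day 29. If a program selects records by visit label, that Day 5 value enters the Visit 6 mean. Read literally, the symptom score would then be the mean of the three days before the exit. This would be an unplanned carry-forward into a result presented as four-week efficacy, and the Visit 6 summaries of IOP, visual acuity and slit lamp findings could be affected in the same way.

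The readable statistics text (Section 9) has no visit window and no rule for early-exit values, and imputation does not reach Visit 6. There is also a smaller worry about Visit 4: an exit near Day 15 in a subject with no Visit 4 record might be filed under Visit 6 and not used for the co-primary hyperemia endpoint.

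**Working it through.** **1. The texts side by side.** Section 5.1.7 names the pages to complete. Section 5.1.6 says when Visit 6 takes place. Section 5.1.8 separates the visit from its assessments: a subject who terminates before Visit 6 has the Visit 6 assessments at an Early Termination Visit. Read together, an endpoint at Visit 6 is a Day 29 ± 1 endpoint, and a Day 10 exit is an early termination recorded on Visit 6 pages. No passage says that records are analysed by form label.

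**2. What is exposed.**
- Both co-primary endpoints are at Visit 4 (Section 3.1) and are multiply imputed if missing (Section 9.4). They do not use Visit 6 values.
- Rescued subjects stay in the study through Visit 6 (Sections 5.2 and 8.4), so inadequate responders who are rescued are not exits.
- Section 5.1.7 covers only exits made at an unscheduled visit.
- Exits with only the minimum set of Section 5.1.8 contribute no hyperemia, gland, staining or break-up-time value under any label.

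**3. The Visit 4 point.** Section 5.1.4 says: "This visit will occur on Day 15 ± 1 day as calculated from Visit 2: Day 1". An exit inside that window can be assigned to Visit 4 by its date. Outside it, Visit 4 is missing and Section 9.4 imputes it. Either way the co-primary is handled.

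**4. The plan's own figure.** Section 9.2 gives 71 per group for 90% power with a two-sided two-group t-test; the effect size and significance level are redacted. At the 0.05 level of Section 9.3, 71 per group implies a standardized effect of 0.548, and an effect of 0.55 returns n = 71 (power 90.2%). The figure is plausible but cannot be checked independently. I use 0.55 below only as an assumed Visit 6 effect.

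**5. Size if records were analysed by label.** Assume equal exits: a share q of Visit 6 records comes from early exits, and these carry a fraction f of the Day 29 effect. The Visit 6 difference is multiplied by 1 − q(1 − f). The documents give neither q nor f.

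| q | f = 0.25 | f = 0.50 | f = 0.75 |
|---|---|---|---|
| 5% | 0.963 | 0.975 | 0.988 |
| 10% | 0.925 | 0.950 | 0.975 |
| 15% | 0.888 | 0.925 | 0.963 |

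For example, q = 10% and f = 0.50 gives 1 − 0.10 × 0.50 = 0.950. If the effect is already complete at exit (f = 1), there is no attenuation.

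**6. Keeping or excluding early values.** Take about 100 per arm (200 randomized, about 1:1) and an assumed Visit 6 effect of 0.55. Keeping q of the records at a fraction f gives an effect of 0.55 × [1 − q(1 − f)] with 100 per arm. Excluding them leaves 0.55 with 100(1 − q) per arm.

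| q | keep, f = 0.5 | keep, f = 0 | exclude |
|---|---|---|---|
| 5% | 96.5% | 95.7% | 96.5% |
| 10% | 95.7% | 93.6% | 95.6% |
| 15% | 94.7% | 90.8% | 94.6% |

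Power is only a yardstick here, because the Visit 6 comparison is descriptive. At f = 0.5 the choice makes no practical difference. At f = 0 it costs between 0.8 and 3.8 points.

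**The case for a change.** The strongest reply is that this goes beyond silence about visit windows: Section 5.1.7 itself creates the mismatch between label and timing. Exits also need not be equal. Assume Day 29 improvements of 1.5 (active) and 1.0 (vehicle), with exit values at half of these. Exits of 5% active and 15% vehicle give 1.5 × 0.975 − 1.0 × 0.925 = 0.54 against a true 0.50; the reverse gives 1.5 × 0.925 − 1.0 × 0.975 = 0.41. The direction is not known in advance, so the bias cannot be called conservative. A rule set before unmasking would cost one or two sentences and would prevent a later choice made with the data in view.

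Part of this stands. The mismatch is real, the readable text does not resolve it, and a descriptive estimate labelled Day 29 should be one. The unequal-exit figures carry little weight, because they need a threefold imbalance that nothing in the documents suggests, as well as analysis by label. Imbalance would also be visible: Section 9.1.1 summarises disposition by study group, and Section 9.4 looks at reasons for missing data and at differences between groups. Section 9.1.2 foresees a clinical data review before unmasking, when visit assignment can be settled.

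An added rule would not be a clear gain either. Removing early values from Visit 6, with no imputation there, moves that analysis towards completers. Such a rule would also need a window: taken as Day 29 ± 1, it would drop ordinary visits that run late, such as Day 31.

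**Conclusion.** No change is needed. This is a missing detail of the kind analysts fill by deriving the analysis visit from the assessment date, and the separate SAP or the redacted part of Section 9.1.2 may already cover it. The co-primary conclusion at Visit 4 is not affected, and no error rate is at stake at Visit 6.

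The possible harm is an attenuation of about 1% to 11% in a descriptive Visit 6 difference. It requires that early-exit records are analysed as Visit 6, that they make up 5% to 15% of each arm (about 5 to 15 subjects of 100), and that they carry 25% to 75% of the Day 29 effect. All three are assumptions. Unequal exits could move the estimate either way, but the documents give no basis for a size. The conclusion assumes that assessment dates are recorded with the data and that exits are reported by arm.

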5.1.8. Early Termination Visit

In the event of termination prior to Visit 6, every attempt will be made to ensure that all Visit 6 assessments are performed. If this is not feasible, at least the following should be performed/assessed:

- Use of any concomitant medications since the last visit
- Occurrence of any AEs since the last visit
- Used and unused investigational product collected and compliance assessed [REDACTED]
- Subject-rated assessment of ocular discomfort
- BCVA
- Slit lamp biomicroscopy
- IOP measurement

5.2. RESCUE MEDICATION USE

Any subjects not responding adequately to the study medication may be rescued and placed on alternate therapy at the Investigator's discretion at any time. The choice of rescue medication is at the Investigator's discretion. Any subject placed on rescue therapy will discontinue use of the study medication and continue study participation through Visit 6. Rescued subjects will be considered treatment failures, but the need for rescue therapy will not be considered an AE. Rescued subjects experiencing an AE at the time of rescue will be followed through stabilization or resolution of the AE or the end of the study (whichever comes last). Rescued subjects should not be withdrawn from the study, but rather followed to resolution of signs and symptoms or until the Investigator has deemed the subject is stable.

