4.2. SUBJECT EXCLUSION CRITERIA

In order for subjects to be eligible at Visit 1 and Visit 2 they may not:

- 1. Have known hypersensitivity or contraindication to the investigational product(s) or their components.
- 2. Have used any of the following medications within 30 days prior to Screening (Visit 1) and for the duration of the study:
 - a. Ocular, inhaled, or intranasal corticosteroids
 - b. Ocular or oral NSAIDs with the exception of low dose aspirin (≤ 81 mg per day)
 - c. Topical ocular antibiotics
 - d. Topical ocular antihistamines or mast cell stabilizers
 - e. Oral antihistamines
 - f. Topical or nasal vasoconstrictors
- 3. Have used any of the following medications within 60 days prior to Screening (Visit 1) and for the duration of the study:
 - a. Topical cyclosporine (Restasis®)

- b. Any form of topical LE
4. Have altered oral dosing of the following within 30 days prior to Screening (Visit 1) or anticipate alteration of dosing during the study:
 - a. Tetracycline compounds (e.g., tetracycline, doxycycline, or minocycline)
 - b. Omega-3 or Omega-6 supplements
5. Have altered dosing of the following medications within 6 months prior to Screening (Visit 1) or anticipate alteration of dosing during the study:
 - a. Anticholinergics
 - b. Antidepressants
 - c. Isotretinoin
 - d. Oral corticosteroids
 - e. Systemic immunosuppressive agents
6. Be unwilling to abstain from the use of any topical ophthalmic medications at Visit 1 (Screening) and for the duration of the study, including:
 - a. Eyelash growth medications
 - b. Eye drops, gels, or artificial tears
7. Be unwilling to abstain from the use of TNF-blocking agents (e.g. etanercept, adalimumab, infliximab) at Visit 1 (Screening) and for the duration of the study.
8. Be currently receiving treatment for glaucoma, have history of or current glaucoma, or an IOP over 21mmHg at Visit 1 (Screening) or Visit 2 (Randomization).
9. Initiate or alter the use (if using upon entry) of oral contraceptives, or female hormone replacement therapy/supplementation within 48 hours prior to Visit 1 and for the duration of the study.
10. Be unwilling to abstain from wearing contact lenses for 14 days prior to Visit 1 and throughout the study.
11. Be monocular or have a BCVA, using corrective lenses if necessary, of +1.0 logMAR or worse as assessed by ETDRS.
12. Be unwilling to discontinue warm compress therapy, lid expression, or lid massage 14 days prior to Day 1 and for the duration of the study.

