6.2.1. Permitted Medications and Therapies

Medications and therapies not specifically excluded in [Section 6.2.2](#) may be taken as necessary.

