6.2.2. Medications and Procedures Not Permitted

The following procedures and medications are not allowed for the time periods specified.

Within 14 ± 1 days prior to Visit 1 (Screening) and for the duration of the study:

- Warm compresses
- Lid margin expression

- Lid margin massage

From Visit 1 (Screening) and for the duration of the study:

- Eyelash growth medications
- Eye drops, gels, or artificial tears (including glaucoma medications)
- Any other topical ophthalmic medication
- TNF-blocking agents (e.g. etanercept, adalimumab, infliximab)

Within 48 hours prior to Visit 1 (Screening) and for the duration of the study, initiate or alter use of:

- Oral contraceptives, and female hormone replacement therapy/supplementation

Within 30 days prior to Screening (Visit 1) and for the duration of the study:

- Ocular, inhaled, or intranasal corticosteroids
- Ocular or oral NSAIDs with the exception of low dose aspirin (≤ 81 mg per day)
- Topical ocular antibiotics
- Topical ocular antihistamines or mast cell stabilizers
- Oral antihistamines
- Topical or nasal vasoconstrictors

Within 30 prior to Visit 1 (Screening), have altered or anticipate alteration of:

- Oral dosing of tetracycline compounds (e.g., tetracycline, doxycycline, or minocycline).
- Omega-3 or Omega-6 supplements

Within 60 days prior to Screening (Visit 1) and for the duration of the study:

- Topical cyclosporine (Restasis[®])
- Any form of topical LE

Within 6 months prior to Screening (Visit 1) have altered or anticipate alteration of dosing during the study:

- Anticholinergics
- Antidepressants
- Isotretinoin
- Oral corticosteroids
- Systemic immunosuppressive agents

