8.4. RESCUE THERAPY

Any subjects not responding adequately to the study medication may be rescued and placed on alternate therapy at the Investigator's discretion at any time. The choice of rescue medication is at the Investigator's discretion. Any subject placed on rescue therapy will discontinue use of the study medication and continue study participation through Visit 6. Rescued subjects will be considered treatment failures, but the need for rescue therapy will not be considered an AE. Rescued subjects experiencing an AE at the time of rescue will be

followed through stabilization or resolution of the AE or the end of the study (whichever comes last).

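### Does investigator-chosen rescue (5.2, 8.4) collide with the not-permitted list (6.2.2) in a way that undermines the Visit 4 analysis?

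*Combined protocol and SAP*

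**What the plan says.** Section 5.2, largely repeated in 8.4, allows a subject who responds inadequately to be rescued at any point. On the therapy: "The choice of rescue medication is at the Investigator's discretion". On what follows: "Any subject placed on rescue therapy will discontinue use of the study medication and continue study participation through Visit 6". Section 5.2 adds: "Rescued subjects should not be withdrawn from the study". Both sections give the status: "Rescued subjects will be considered treatment failures, but the need for rescue therapy will not be considered an AE".

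Section 6.2.2 begins: "The following procedures and medications are not allowed for the time periods specified". From screening to the end of the study its list covers eye drops, gels and artificial tears and then "Any other topical ophthalmic medication". Other entries bar ocular corticosteroids, topical cyclosporine, topical loteprednol, warm compresses, lid expression and lid massage. Section 6.2.1 allows, as needed, "Medications and therapies not specifically excluded in" 6.2.2. Exclusion criterion 6 in section 4.2 reads in part: "Be unwilling to abstain from the use of any topical ophthalmic medications at Visit 1 (Screening) and for the duration of the study". Criteria 2, 3 and 12 are similar. None of these places mentions rescue, and 5.2 and 8.4 do not mention 6.2.2.

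On analysis, 9.1.2 defines ITT as all randomized subjects. Section 3.1 compares means at Visit 4, and 9.3 requires both co-primaries to reach 0.05. Section 9.4 applies multiple imputation under MAR to the co-primaries. Parts of 9.1.2 are redacted, and the Efficacy Evaluable (EE) definition is deferred to a SAP whose text is not in the public document.

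**The concern.** Read literally, a subject rescued with an eye drop is retained as a treatment failure under 5.2 and is also using a disallowed medication under 6.2.2. Section 5.3 item 5 lists failure to comply with protocol requirements among the reasons for discontinuation. One site might then keep such a subject and record a Visit 4 score after rescue, while another discontinues the subject. In the second case 5.1.7 sends the data to the Visit 6 forms, Visit 4 is missing, and 9.4 imputes it. If rescue were common before Day 15 and unequal between arms, the two routes could give different co-primary estimates. The treatment-failure label also has no visible role in a comparison of means.

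**Working it through.** **Do the passages give two competing rules?**

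| Point | 5.2 / 8.4 | 6.2.1 / 6.2.2 | 4.2 | 5.3 item 5 |
|---|---|---|---|---|
| Subject matter | Rescue | Concomitant medication in general | Eligibility at Visits 1 and 2 | The subject's own non-compliance |
| Force | Stop study drug, stay to Visit 6; 5.2 says not to withdraw | Disallows listed items; silent on rescue | Criteria 6 and 12 concern unwillingness at entry; 2 and 3 extend over the study but sit under the eligibility heading | Permissive |

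Only the first column addresses a rescued subject. Rescue is an act of the investigator that 5.2 authorises, so it does not fit easily under a subject's failure to comply. Section 5.3 does not require withdrawal, and 5.2 speaks against it. A rescue therapy that is not on the 6.2.2 list breaches nothing. What is left is the status, exception or deviation, of a listed therapy given as rescue.

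**What does the readable text imply for analysis?** A rescued subject is randomized, hence in ITT. The subject is retained, hence has a Visit 4 score. That score is observed, hence not imputed under 9.4.

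**How large could the effect be?** Section 9.2 gives 71 per group and 90% power; its effect size and significance level are redacted. Taking two-sided 0.05 from 9.3:

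- Normal approximation: d = (1.960 + 1.282) × √(2/71) = 0.544. The t-test gives 0.548.
- If the redacted level were 0.025 or 0.01, d would be 0.597 or 0.655.
- Check: d = 0.55 needs n = 70.4, rounded up to 71, with power 90.2%. This agrees with the plan but is a back-calculation.
- About 200 randomized gives about 100 per group; power per co-primary is then 97%.

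Let p_v and p_a be the proportions rescued before Visit 4 (vehicle, active) and b the rescue benefit in SD. If scores after rescue are used as recorded, the difference is d − b(p_v − p_a). All rates and benefits below are assumptions.

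| p_v / p_a | b = 0.25 | b = 0.5 | Power at 100 per group |
|---|---|---|---|
| 2% / 1% | 0.548 − 0.0025 = 0.546 | 0.548 − 0.005 = 0.543 | essentially unchanged |
| 10% / 3% | 0.548 − 0.0175 = 0.531 | 0.548 − 0.035 = 0.513 | 95-97% |
| 20% / 5% | 0.548 − 0.0375 = 0.511 | 0.548 − 0.075 = 0.473 | 90-96% |
| 5% / 10% | 0.548 + 0.0125 = 0.561 | 0.548 + 0.025 = 0.573 | not below 97% |

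The ranges in the two middle rows come from simulation, with rescue either at random or of the worst scorers. The standard error of the difference at 100 per group is √(2/100) = 0.141 SD, so a shift of 0.035 is about a quarter of one standard error.

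If every rescued subject were instead discontinued and Visit 4 imputed from Visit 2 (correlation 0.5, assumed), simulated power at 100 per group is 96-97% at 2%/1%, 89-95% at 10%/3% and 71-95% at 20%/5%. The low ends need rescue of exactly the worst Visit 4 scorers.

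**The case for a change.** The strongest case for acting is that the conflict can be read directly and touches ordinary practice. Section 1 names five MGD treatments. Section 6.2.2 bars three of them (massage, lid expression, topical cyclosporine) and restricts dosing changes for the other two (tetracycline, doxycycline). Nothing says that 5.2 is an exception. Section 5.3 leaves discontinuation to discretion, so sites could differ. A subject who leaves early may have no hyperemia score, because the minimum set in 5.1.8 omits the investigator-rated signs. Agreeing the handling before unmasking would be cheap.

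Part of this stands. The text does not settle whether listed rescue is a deviation, and that may matter for the EE set. But section 1 does not claim to list every treatment, and discontinuing someone because of authorised rescue would go against 5.2. The window is short: only rescue between Day 1 and Day 15 can alter Visit 4, and the one scheduled visit in between (Visit 3) lists no investigator-rated signs. Section 9.4 already has reasons for missing data recorded and their effect, with any arm imbalance, weighed against MAR. Section 6.2 records every medication with dates and indication, so rescue by arm and visit can be tabulated from data already collected. How treatment failures enter the comparison may be stated in the redacted part of 9.1.2 or in the SAP, and its absence from the readable text is not evidence that the plan lacks it.

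**Conclusion.** No change to the statistical plan is called for. Sections 5.2 and 8.4 must be reconciled with 6.2.1 and 6.2.2, which a cross-reference would do; I take no view on which clinical rule is right. For the primary analysis this is a gap that analysts can fill from the existing text: ITT, retention after rescue, and imputation only where Visit 4 is missing. No wrong result follows from that reading, and asking for a written rule or an added sensitivity analysis would not supply a better method.

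The size rests wholly on assumed rescue rates, selection, benefit and correlation, and on a significance level taken from 9.3. With scores after rescue used as recorded, the shift is at most 0.075 SD in the cases shown and close to nil if early rescue is rare. The 100-per-group figures would not carry over to hyperemia if its redacted qualifier restricts that endpoint to a Visit 2 subset. I would reconsider if the SAP were shown to handle rescued subjects inconsistently, or if rescue before Visit 4 turned out to be frequent and unbalanced.

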3. TRIAL DESIGN

3.1. PRIMARY EFFICACY ENDPOINTS

Comparison of mean [REDACTED] Severity Assessment Score between the KPI-121 0.25% ophthalmic suspension group and the vehicle group:

- Visit 4 (based on the mean score for the 3 days prior to Visit 4)

Comparison of mean posterior lid margin hyperemia [REDACTED]

[REDACTED] at Visit 2 between the KPI-121 0.25% ophthalmic suspension group and the vehicle group:

- Visit 4

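### Does the plan need a rule for how Visit 4 scores obtained after rescue enter the co-primary comparisons?

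*Combined protocol and SAP*

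**What the plan says.** Section 5.2 lets the investigator rescue a subject at any time with a medication of the investigator's choice. Study medication then stops and participation continues through Visit 6. On status it says: "Rescued subjects will be considered treatment failures, but the need for rescue therapy will not be considered an AE". On follow-up it says: "Rescued subjects should not be withdrawn from the study, but rather followed to resolution of signs and symptoms". Section 8.4 repeats the status: "Rescued subjects will be considered treatment failures".

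Both co-primary endpoints in 3.1 are comparisons of means at Visit 4. The symptom score is taken at "Visit 4 (based on the mean score for the 3 days prior to Visit 4"; the sign is posterior lid margin hyperemia, with part of its definition redacted.

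Section 9.1.2 states: "The primary analysis population will be the Intent-to-Treat (ITT) population, defined as all subjects randomized". The text directly after this is redacted. The definition of the Efficacy Evaluable population is to be "outlined in the Statistical Analysis Plan and finalized prior to unmasking of study data".

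Section 9.4 begins: "Any missing, unused, or spurious data will be noted in the final clinical study report". It then provides multiple imputation for incomplete data under a missing-at-random assumption and limits its reach: "Imputation will be carried out only on the co-primary endpoints and time points".

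**The concern.** Rescue can come before Visit 4, and a rescued subject can still have a Visit 4 score. That score partly reflects another therapy. Calling the subject a treatment failure suggests that the score should not count at face value, yet no visible endpoint or analysis text uses the label. Three readings seem open:

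1. Use the score as observed.
2. Replace it under a failure rule.
3. Set it aside and impute it, taking it as part of the unused data named in 9.4.

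These answer different questions and can give different p-values on the same data. If the choice were made after unmasking, the most favourable could be picked. A side issue is that 6.2.2 bars other topical ophthalmic medication with no visible exception for rescue, so a rescue drop might be coded as a prohibited medication.

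**Working it through.** **Reading the sections together.** The three readings do not have equal support.

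- *Observed.* 9.1.2 analyses everyone randomized; 5.2 and 8.4 keep rescued subjects in follow-up; 9.4 imputes only what is incomplete. A recorded score is not incomplete. Nothing further is needed to run this analysis, even when rescue falls inside the three-day averaging window.
- *Failure rule.* This needs a replacement value, and none is visible. The co-primaries are means, with no responder or failure endpoint. The label stands in the two sections on rescue, in a sentence that separates rescue from adverse events.
- *Imputed.* This rests on one word in 9.4. In that sentence unused data are to be noted in the study report; the imputation sentence speaks of incomplete and missing data.

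**The plan's own figure.** 9.2 gives 71 per group and 90% power with a two-sided t-test; the effect size and level are redacted. With the 5% level of 9.3, the noncentral t gives an effect of 0.548 SD. This is back-solved, so it is an inference. At about 100 per arm (200 randomized, 1:1) the same effect has 97.1% power.

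**How far apart the readings can be.** No rescue rate or rescue benefit is given; all values below are assumptions. At 100 per arm the standard error of the difference is √(2/100) = 0.141 SD. The gap between the observed reading and one that undoes the rescue benefit is

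(vehicle rate × vehicle benefit) − (drug rate × drug benefit).

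- 5% vs 2%, benefit 0.5 SD: 0.025 − 0.010 = 0.015 SD, or 0.11 standard errors. A result at p = 0.05 moves to 0.039 or 0.064.
- 10% vs 3%, benefit 1 SD: 0.10 − 0.03 = 0.07 SD, or 0.49 standard errors. A result at p = 0.05 moves to 0.014 or 0.14.
- Equal rates and equal benefits: gap zero. More rescue on drug reverses the sign.

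Measured against a trial with no rescue, and holding the SD fixed, the 10% vs 3% case takes a planned difference of 0.55 SD to 0.55 − 0.07 = 0.48 SD. Power at 100 per arm goes from 97.2% to 92.2%.

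**Simulation of the symptom endpoint, 100 per arm.** Scores are normal with unit SD. Correlations are 0.6 (Visits 2–3), 0.6 (Visits 3–4) and 0.5 (Visits 2–4). The drug effect is 0.548 SD at Visit 4 and half that at Visit 3. Subjects with the worst Visit 3 scores are rescued, with a benefit of 0 to 1 SD. The failure rule is the worse of the Visit 2 and Visit 3 scores, an illustration that appears nowhere in the documents. The table gives the share of trials in which readings disagree on significance.

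| Rescued before Visit 4, vehicle vs drug | Any of the three disagree | Observed vs imputed only |
|---|---|---|
| 2% vs 1% | about 2% | about 1% |
| 5% vs 3% | 2–4% | 1–2% |
| 10% vs 6% | 4–6% | 2% |
| 20% vs 13% | 9–12% | 5–7% |

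At 10% vs 6%, power is about 97% for observed scores, 93–95% for the failure rule and 95–96% for imputation. Rescue pulls in extreme scores and so trims the SD, which is why observed use loses less here than the fixed-SD figure suggests.

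**False positives.** With no drug effect and equal rescue, each reading favours drug wrongly in 2.1–2.8% of trials, against a nominal 2.5%. Picking the best of the three after unmasking gives 3.0–3.5% at 2% rescue, rising to 4.2–4.9% at 20%. This matters only if the other co-primary truly works, because 9.3 requires both to succeed.

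**The case for a change.** The strongest case for a change is that intent-to-treat fixes who is analysed, not which value is used after rescue. Observed use is nowhere stated, and it leaves the failure label with no part in the primary comparison. 9.4 does not define unused data. 9.1.2 expressly sends the Efficacy Evaluable definition to the SAP, but no visible text does so for post-rescue scores. With 20% vs 13% rescued, the three readings disagree in 9–12% of trials at 100 per arm and 19–22% at 71 per arm. A sentence would cost little.

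Much of this stands as description: the visible text is silent, and a line in the SAP would be tidy. It does not show that the plan goes wrong. The silence falls where text is blacked out, and the SAP that 9.1.2 and 9.5 refer to is not supplied, so absence cannot be inferred. A label with no part in the primary test can still serve the Efficacy Evaluable set or descriptive reporting. About half of the three-way disagreement comes from the illustrative failure rule. It also hardly depends on rescue benefit (4.9% with none and 5.0% with 1 SD, at 10% rescue), so most of it reflects replacing values near the significance threshold. The 71-per-arm figures use the powering minimum, not the roughly 100 per arm planned. Nothing in the documents supports 20% rescue within two weeks.

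As to a choice made after unmasking, 6.5 withholds the code until database lock unless there is medical need, 9.1.2 foresees a data review before unmasking, and 9.5 requires deviations from the SAP to be described and justified.

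On identifying rescue, 6.2 records drug, dates, indication and any link to an adverse event, and 5.2 ties rescue to stopping study medication. Sections 5.2 and 6.2.2 do not fit together literally and must be reconciled in wording. That is a separate matter: under the visible intent-to-treat definition the subject is analysed either way.

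**Conclusion.** No change to the analysis follows. This is a gap that analysts fill sensibly: the visible text leads to using Visit 4 scores as recorded, which is valid, holds its error rate and gives up no power to the alternatives tried. The other readings would need rules that the visible text does not contain. Either approach would be acceptable as primary if fixed before unmasking, so the concern identifies no stated rule that yields a wrong result; it asks for detail.

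The size is unknown, because no rescue rate is given. Under the simulation's assumptions, with up to 10% of vehicle subjects rescued before Visit 4 and 100 per arm, observed and imputed scores disagree on significance in about 2% of trials or fewer. The conclusion rests on the inferred effect of 0.548 SD, the assumed rescue rates and benefits, and the symptom endpoint alone; the hyperemia analysis set is redacted. It would need another look if the SAP or the redacted text set a rule that conflicts with the visible text, or if rescue before Visit 4 proved frequent and unequal between arms.
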